Type of Risk	Level of Risk	Risk and Occurrence
Lead Implant Risks	Possible	Lead migration (13.2%) Failure/malfunction of leads (9.1%) Superficial site infection (4.5%) Procedure complications, including infection & fever (3.4%)
	Unlikely	Persistent pain at lead implant site (0.9%) Temporary pain at implant site (0.9%) Tissue reaction to leads (0.3%) Epidural hematoma (0.3%) Skin erosion around the leads (0.2%)
	Very Unlikely	Allergic reaction to leads (0.1%) Paralysis (0.003%) Nerve injury Death
Stimulation Risks	Possible	Malfunction of stimulation system (4.5%) Undesirable sensations (2.4%) Increased pain in area other than implant site Uncomfortable stimulation of tissue around leads Development of pain in a new location
	Unlikely	Increase in pain intensity, duration, or frequency
	Very Unlikely	Seizure Paralysis Nerve injury Death

2.2 Benefits:

Because of the short-term of the study, there is no opportunity for long-term benefits to patients in this study beyond those associated with the outcome of the trial of conventional SCS therapy. A patient that experiences a successful outcome with trialing conventional SCS therapy

will be eligible for a permanent implant. Participation in this study will provide information that will add to our understanding of treatment options for patients with back pain.

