- 4.2.9** Patients who are undergoing or will undergo therapies or diagnostics that involve electromagnetic fields such as: diathermy based therapies, electrocautery, magnetic resonance imaging (MRI), radiofrequency (RF) or microwave ablation, bone growth stimulators, electrolysis, therapeutic ultrasound, ultrasound, lithotripsy, psychotherapeutic procedures, radiation therapy, and transcutaneous electrical nerve stimulation.
- 4.2.10** A clinically significant disorder such as cerebrovascular disease, pulmonary infarction, ischemic heart disease, cardiac dysrhythmia, myocardial infarction, or congestive heart failure or any other as determined by the investigator
- 4.2.11** Uncontrolled diabetes, uncontrolled pulmonary disease, or uncontrolled hypertension
- 4.2.12** Patients who have evidence of major psychiatric disease, mental disorder, drug dependency, alcohol dependency, or substance abuse disorders
- 4.2.13** Patients who have progressive neurological disease such as multiple sclerosis, chronic inflammatory demyelinating polyneuropathy, rapidly progressive arachnoiditis, acute herniated disc, or any other as determined by investigator
- 4.2.14** Medical condition or pain condition in other body areas that could interfere with study procedures, accurate pain reporting, and/or confound evaluation of study end points
- 4.2.15** Concurrent participation in another clinical study
- 4.2.16** Involvement in an injury claim under current litigation or a pending or approved workers' compensation claim

4.3 Withdrawal:

Subjects may voluntarily withdraw from the study at any time. Withdrawing from the trial will not carry out any sanction and will not affect patient's access to other treatments.

4.4 Terminating Participation:

A patient's participation in the study may be terminated if continued participation in the study is not in the subject's best interest, according to the Principal Investigator's opinion or if the subject withdraws participation from the study. Therapy will be stopped and leads will be removed. Any patient who suffers an adverse event whether or not related to study treatment may withdraw voluntarily from the study.

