5.3 Clinic Visit 1: Enrollment/Baseline Visit

A patient will be enrolled in the study upon signing the ICF, verifying that all inclusion and exclusion criteria are met (using CRF01) and reaffirming voluntary participation, and. Medical history, including pain management, and baseline pain will be collected and recorded in the appropriate CRFs (CRF02, CRF03, and CRF04).

5.4 Clinic Visit 2: Lead Implantation, Conventional SCS Programming and Training Procedure:

Patients will be implanted with commercially available temporary leads as part of the regular SCS trial period and using standard clinical practice. The patient will be placed on a surgical bed in a supine position and may be mildly sedated. The back of the patient will be draped and cleaned using sterile techniques. A properly trained physician will guide and place two percutaneous leads into the epidural space using introducers and steering stylets while under fluoroscopic x-ray guidance. Once the leads are placed above the dorsal aspect of the cord at the proper vertebral level, the introducers and stylets are removed. The exterior portion of the leads will be anchored with sutures or taped firmly to the skin and the proximal ends of the leads connected to an interface cable, which will be plugged into the ENS. The leads and cables will be properly secured to minimize migration of the leads and prevent accidental disconnection. An AP and lateral radiograph of the implanted leads in reference to the vertebral levels will be collected. After the patient has recovered from sedation, programming of conventional SCS therapy will be performed using standard clinical practice.

5.4.1 Conventional SCS Therapy:

For Conventional SCS Therapy, the ENS will be programmed to deliver pulses at a frequency in the 20-200 Hz range with a maximum pulse width of 1 ms. The amplitude of

the electrical signal and the arrays of electrodes used for delivering therapy will be set in order to elicit paresthesia as reported by the patient. Once paresthesia is reported, this will be used to guide the programmer to cover the proper pain dermatome. These parameters and electrode arrangements will be noted and saved in the remote controller. The patient will be educated and trained on operation and troubleshooting the ENS and remote controller.

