Following a satisfactory demonstration on ENS and remote controller operation, the patient will be discharged to home with an emergency 24-hour contact information should the patient have any issues or questions. Programming and training procedure should be approximately 1.5 to 2 hours long. The patient will be scheduled to return to the clinic for the crossover reprogramming visit 4 ± 1 days after the initial programming.

5.5 Clinic Visit 3: Crossover visit:

After 4 ± 1 days of trialing conventional SCS therapy, the patient will return to the clinic for a reassessment of the lead location using x-ray fluoroscopy, and crossover to PM-SCS therapy. Pain level obtained with conventional SCS will be assessed and recorded in CRF05 before crossing over to PM-SCS therapy. The study physician may reposition the leads if deemed necessary upon comparison to the initial x-ray image. If leads have migrated and cannot be re-adjusted, the patient will be exited from the study and subject data will be excluded from the final analysis. After x-ray assessment, stimulation parameters will be programmed as described below for PM-SCS. No therapy will be given for up to one day to allow washout of the conventional SCS therapy.

5.5.1 Polymodal SCS Therapy:

In this case the ENS will be programmed to deliver multiple simultaneous signals with different stimulation parameters to different electrode arrays in the leads. Stimulation signals will be in the 20-1,200 Hz range and a maximum pulse width of 1 ms, which is within the CE Mark and FDA approved parameters. The parameters of each program will be saved in the remote controller. The patient will be educated and trained on operation and troubleshooting the ENS and remote controller as it pertains to PM-SCS therapy.

5.6 Standard of Care Follow up phone visits:

It is standard practice that during a SCS trial period, a Clinical Field Technician (CFT) will contact the patient by phone to track the status of therapy and comfort of the patient.

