Accordingly, follow up phone visits will be performed as needed during the study. After the first day of therapy and depending on the extent of pain relief reported by the patient, the CFT may instruct the patient to adjust the level of stimulation as deemed appropriate by patient to obtain optimum pain relief. The patient may also be instructed to use a different therapy group in case a therapy cannot be optimized with the previously tried therapy group. This process may be repeated during trial days for both the conventional SCS part of the trial and the PM-SCS part of the trial. Depending on feedback from the phone visits, the PI may decide to schedule a visit to the clinic for reassessing lead position and reprogramming, or to address an adverse event.

5.7 Optional unscheduled clinic visit:

If lead migration is suspected, the PI may schedule a reprogramming visit. In this visit, the PI may evaluate the position of the leads inside the epidural space using x-ray fluoroscopy and reposition and/or reprogram as needed. The PI may also change stimulation parameters using patient feedback as done during the initial visit or during the crossover visit. This visit may also be used to address any other mild or moderate adverse events related to SCS therapy.

5.8 Clinic Visit 4: End of trial period visit:

The patient will return to the clinic as scheduled for an end of trial period visit, in which the stimulation will be stopped, the hardware disconnected from the leads, and the temporary leads removed. Before stimulation is stopped, the patient will be asked to provide feedback about pain status, subjective satisfaction, and paresthesia sensation, which will be recorded in the appropriate CRFs (CRF06, CRF07, and CRF08). This visit may take place any time if the PI deems necessary to exit a patient from the trial and study, or if the patient voluntarily decides to withdraw.

5.9 Other therapies:

As per standard of care practice the patient may continue on prophylactic antibiotics as prevention for bacterial skin infection. Patient will also follow the investigating physician's protocol for anticoagulant therapy, other medications, as well as over-the-counter medications and supplements.

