6.3 Safety

Adverse events (AE) related to the stimulation therapies will be tracked during the study period to address any safety outcomes. Any AE encountered using the conventional SCS therapy will also be noted in the patient's medical history. All device and/or procedural adverse events will be reported.

AEs will be tracked and categorized by the PI as related to implant (leads) or activation of the stimulation program. It is expected that the polymodal SCS will have a safety profile similar to conventional SCS.

All AEs will be recorded in the corresponding Case Report Form (CRF). The PI will also rate the AE in terms of its severity. Any AE considered by the PI to be a serious adverse event (SAE) will be reported immediately (within 24 hours) to the sponsor and to the IRB within five (5) days after the PI first learns of the event.

6.3.1 Adverse Events (AEs):

The following is a list of potential adverse events associated to SCS therapy and the indwelling leads with reported risk and frequency of occurrence:

- Related to Lead implant:
 - Movement of lead (possible, 13.2%)
 - Malfunction or failure of lead (possible, 9.1%)
 - Superficial site infection (possible, 4.5%)
 - Complications related to implantation procedure including infection; fever (possible, 3.4%)
 - Persistent or temporary pain at the implant site (unlikely, 1.8%)
 - Tissue reaction to leads (unlikely, 0.3%)
 - Hematoma (unlikely, 0.3%)
 - Bleeding (unlikely, 0.3%)
 - Skin erosion over the leads (unlikely, 0.2%)
 - Allergic reactions to leads (very unlikely, 0.1 %)
 - Paralysis (very unlikely)
 - Nerve injury (very unlikely)
 - Death (very unlikely)
- Related to stimulation:
 - Malfunction of stimulation system (possible, 4.5%)

- Undesirable sensations (possible, 2.4%)
- Increased pain (possible)
- Uncomfortable stimulation of tissue around the leads (possible)
- Development of pain symptoms in a new location (possible)
- Increase in pain intensity, duration, or frequency (unlikely)
- Seizure (very unlikely)
- Paralysis (very unlikely)
- Nerve injury (very unlikely)
- Death (very unlikely)

AEs related to stimulation with the trialed therapy are expected to be comparable to those associated to others encountered with other SCS therapies (such as HF-10 or Burst) or ENS.

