7. DEVICES

7.1 Stimulation leads:

Commercially available SCS leads will be used. Since leads are manufactured with variable dimensions and number of electrode arrays, the study will utilize leads with the following specifications in order to avoid outcome variability. The patient will be implanted with two in line eight-contact percutaneous cylindrical leads, each with a diameter of 1.3 mm, an edge-to-edge inter-electrode distance of 6 mm or 4 mm, and an electrode length of 3 mm. These specifications are met by leads available from Medtronic (Minneapolis, MN, USA; Reference 3873 1x8 Standard or 3874 1 x 8 Compact). The same leads will be used during both conventional and polymodal SCS therapy.

7.2 Multi-lead trialing cable:

The proximal end of each lead is terminated by eight metal contacts that deliver electrical signals to the electrodes in the distal end. These contacts are interfaced to an ENS unit using a cable that is fully compatible with both the stimulation leads and ENS unit. A commercially

Trialing of PM modulation therapy in patients with chronic intractable back pain with or without leg pain.
Protocol # [REDACTED]

available cable from Medtronic (Minneapolis, MN, USA; Reference 355531) will be used. The same cable will be used during either conventional or polymodal SCS therapy.

7.3 External Trial Stimulator (ENS) unit:

The trialing cable is connected to the ENS unit which is the device that delivers the stimulating electrical signals. A commercially available external trial neurostimulator from Medtronic (Minneapolis, MN, USA; Reference 37022) will be used during the conventional SCS. An investigational device based on this commercial unit will be used for PM-SCS (Medtronic, Minneapolis, MN, USA; Reference 37022-MRS). [REDACTED]

[REDACTED]

[REDACTED]

[REDACTED]

[REDACTED]

[REDACTED]

7.4 Clinician Programmer:

The ENS unit is programmed by a trained CFT using a computer-based interface and software. The programmer is fully compatible with the ENS unit described above and uses short-distance telemetry protocols to safely communicate with the ENS unit. For conventional SCS, commercially available N'Vision® Clinician Programmer (Medtronic, Minneapolis, MN, USA; Reference Model 8840) will be used by the CFT or clinician to program the commercial ENS unit.

[REDACTED]

[REDACTED]

[REDACTED]

[REDACTED]

7.5 Patient Remote Controller:

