Spinal cord stimulation therapy (either conventional SCS or PM-SCS) can be adjusted by the patient using the parameters set by the clinician during programming. This can be done using a handheld device that communicates with the ENS via short-distance telemetry. The remote controller allows the patient to turn the therapy on or off, adjust the level of stimulation (i.e. the amplitude of the electric field), and switch from a therapy group to other one as previously set by the CFT and clinician. The patient remote controller is fully compatible with both the ENS, and the clinician programmer described above. A commercially available device from Medtronic (Minneapolis, MN, USA; Reference MyStim® 97740) will be provided to the patient to carry on during the trial. The CFT will train the patient on using the remote controller and will provide

printed operating instructions as well as contact information in case the patient should have any questions about operating the device. Refer to Appendix D2 for a detailed product description.

7.6 Device Accountability Procedures:

All non-disposable devices (ENS, patient remote controller, and clinician programmer) will be under the control of the CFT who will program the ENS once the leads have been attached to it. The serial numbers of the investigational ENS and remote controller will be annotated in the corresponding CRF (CRF10). The CFT will be available 24-hours a day at a location near the study site during the length of the therapy. The CFT will retrieve the devices once a subject has completed therapy or exited the study. No devices will be left in the custody of the study site; thus study sites will not carry an inventory of devices.

Use of an investigational device outside the described study protocol is strictly forbidden and will constitute grounds for removal of the operator or institution from the study.

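### On withdrawal, section 4.4 stops therapy and removes the leads, with no exception for a subject who leaves only the research during the standard-care conventional SCS period

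*Combined protocol and SAP*

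**What the plan says.** Section 4.4 (Terminating Participation) gives two grounds for ending participation. One is the investigator's judgement of the subject's best interest. The other, with the consequence that follows, reads: "or if the subject withdraws participation from the study. Therapy will be stopped and leads will be removed". The ending of participation is worded as something that *may* happen; the consequence is worded as something that *will* happen. It is not limited by period or by reason for leaving.

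Section 5.8 (Clinic Visit 4) points the same way. The visit at which stimulation is stopped and the leads come out can be held at any time if the investigator thinks it necessary, "or if the patient voluntarily decides to withdraw".

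Section 4.3 (Withdrawal), immediately before 4.4, assures subjects that leaving brings no sanction and does not affect access to other treatments.

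The first period is described as ordinary care. Section 5.2 recruits patients who have already been approved for an SCS trial. Section 5.4 places commercial leads "as part of the regular SCS trial period and using standard clinical practice". Section 7.3 assigns the commercial stimulator to the conventional period and a separate investigational unit to PM-SCS. Section 7.1 adds: "The same leads will be used during both conventional and polymodal SCS therapy".

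**The concern.** Between Visits 2 and 3 the therapy being delivered is not the investigational one. It is the trial of conventional stimulation that the patient was due to have anyway. Because the leads are shared, removing them on exit from the research also ends that trial.

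This matters to the patient. Section 2.2 says the study offers no long-term benefit beyond what follows from the conventional trial, and that success in that trial makes the patient eligible for a permanent implant. A subject who changes their mind about PM-SCS on day 1 or 2 and formally withdraws would, on the words of 4.4, lose the rest of the part that can benefit them. Resuming would mean a second epidural lead placement. Site staff would also have to choose between the assurance in 4.3 and the instruction in 4.4.

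**Working it through.** No figure in the plan bears on this, so the check is a comparison of the text.

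1. **Is the rule in 4.4 conditional?** No. Subject withdrawal is a named trigger, and stopping therapy and removing leads follow without qualification. Section 5.8 is consistent with this and has no carve-out for the conventional period.

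2. **Is conventional SCS a research procedure here?** The protocol presents it as standard care: approval precedes recruitment (5.2), implantation is part of the regular trial (5.4), and the stimulator is commercial (7.3). PM-SCS comes only after Visit 3 and uses a different stimulator. The research part can therefore be dropped without touching the conventional part, apart from what 4.4 requires.

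3. **Does 4.3 supply the exception?** There are two readings. If *other treatments* includes the ongoing conventional trial, 4.3 and 4.4 contradict each other. If it does not, nothing visible protects that trial. On neither reading does 4.3 say that the leads may stay in.

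4. **Does 7.6 add to the problem?** Only slightly. It says "The CFT will retrieve the devices once a subject has completed therapy or exited the study". This is a device-accountability rule with no deadline, and it does not need changing.

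5. **When does the gap apply?** Section 5.4.1 states: "The patient will be scheduled to return to the clinic for the crossover reprogramming visit", at 4 ± 1 days after initial programming. The window opens at 4 − 1 = 3 days. From day 3, Visit 3 can be held, the conventional pain score recorded (5.5), and PM-SCS declined. The gap is therefore mainly exit after day 1 or day 2.

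6. **Does it touch the endpoint?** The schedule of events takes the NPRS at baseline, at crossover and at end of study, and 6.1 uses the score at the end of each therapy period. A subject who leaves the research on day 1 or 2 has not reached the scheduled conventional score, whether or not the leads stay in afterwards. The analysis is the same under either wording.

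**The case against.** The case for leaving the text alone has five parts.

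- **4.3 and 4.4 can be read together.** On this view 4.3 protects care already approved and 4.4 gives the default exit procedure. The surrounding language is permissive. This softens 4.4, but the sentence on lead removal remains unqualified.
- **The case should be rare.** The visible schedule puts no research procedure between Visits 2 and 3, and section 5.6 describes the phone calls as standard practice. A subject who wants conventional SCS but not PM-SCS has little reason to leave on day 1 or 2. Someone who does leave then may well want stimulation stopped. This stands, and it limits how much the point matters.
- **Unseen text may cover it.** Section 5.2 refers to Appendix A for the consent process; the appendices are redacted and the consent pages are not available. This also stands. If the consent form has the exception, 4.4 still needs to agree with it.
- **Removing temporary percutaneous leads on exit is a sensible safety default.** It is, as a default. An exception at the physician's discretion keeps it.
- **Keeping leads in after research exit raises the question of safety follow-up.** Section 6.3 says "All device and/or procedural adverse events will be reported", but whether that reaches a subject who has left the research depends on the consent wording. The objection is fair, and the fix includes that check.

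A reader might also go further than the documents allow. One inference is that an early leaver counts as a failed SCS trial and loses the route to an implant. No visible section sets a minimum trial length or bars a repeat. Another is that the harm can be quantified from the complication rates in Table 1. Those rates are for SCS in general rather than short temporary leads, and the number of research-only withdrawals is unknown. A third is that withdrawal under 4.4 distorts the comparison of therapies; step 6 of the check shows that the missing wording does not.

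**Conclusion.** The point holds in a narrow form. As worded, 4.4 ends a standard-care SCS trial for a subject who leaves only the research during the conventional period, and this conflicts with the assurance in 4.3. It is a low-priority matter of participant protection and clear instruction to sites. It is confined mainly to exit before Visit 3 can be held, with no effect on the endpoint, the sample size or the analysis.

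The conclusion assumes that 4.4 is followed literally and that no redacted or removed text supplies the exception. An investigator might in practice let the patient finish, but that would depart from the words of 4.4. No frequency is claimed. Confidence is medium, because the consent text cannot be seen.

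**What to change.** In 4.4, extend the sentence on stopping therapy and removing leads with: *, except that a subject who withdraws only from the research during the conventional period may complete the conventional SCS trial on the commercial ENS as standard care, at the treating physician's discretion, and PM-SCS will not be programmed*.

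In 5.8, add a cross-reference to 4.4 where voluntary withdrawal is mentioned. Check that the consent form says the same, including what safety follow-up, if any, applies after exit from the research.

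The cost is one short amendment and the consent check. The downside is a few days of commercial-device and field-technician support for a subject who is no longer in the study. No extra patients or study visits are needed.
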